## **1. METHODS**

### **2.1 Participants**

Veteran outpatients 18 to 50 years of age suffering from PTSD with and without depressive symptoms were recruited from the James A. Haley Veterans' Administration Hospital outpatient clinics and surrounding community. Participants were phone screened for safety and appropriateness of trial. In addition, the clinical information in the Veterans' Administration electronic medical records was reviewed. Veterans eligible to enroll and interested in participating in the study were scheduled for the initial screening/baseline visit and sent a copy of the informed consent. Those found to not be eligible or not interested in the study were referred to their primary mental health clinician or offered contact information for clinical care, if not already established with a provider.

Participants were required to meet all of the inclusion criteria in order to participate in this study, which included being male or female between the ages of 18-50 years. They had to meet DSM-5 criteria for PTSD as determined by clinical interview using CAPS for DSM-5 and have a PTSD checklist for DSM-5 (PCL-5) score greater than or equal to 45. Participants were also required to be on a stable medication regimen and psychotherapy for at least one month as well as be able to maintain this regimen for the duration of the treatment portion of the trial. The stability of the treatment regimen was assessed as part of the baseline history by an experienced psychiatrist. All participants had capacity to provide written informed consent. Candidates meeting any of the exclusion criteria at baseline were excluded from study participation. During the study, veterans could not be enrolled in an acute treatment of PTSD using evidence-based psychotherapy including Prolonged Exposure Therapy (PE), Cognitive Processing Therapy (CPT), or Eye Movement Desensitization and Reprocessing (EMDR). For safety reasons, the

standard exclusions for rTMS studies were applied and included: any metal or device implants that would increase risk of rTMS; history of epilepsy or seizure disorder, mass brain lesions, cerebrovascular accident, metal in the skull, a history of major head trauma defined as greater than mild TBI; any neurologic or medical condition likely to increase risk of rTMS; taking any medication that significantly lowered the seizure threshold (e.g., stimulants, tricyclic antidepressants (TCA), theophylline, first generation antipsychotics, etc.); or inability to determine the motor threshold in the subject. Many psychiatric comorbidities were allowed with the exceptions of: suicidal risk that precludes safe participation defined as clinical impression that the subject is at significant risk for suicide; lifetime history of schizophrenia, schizoaffective, other psychotic disorder, bipolar disorder type I or II, dementia, or dissociative disorders; personality disorder so severe that participant would be unlikely to be able to complete study protocol requirements; and history of problematic Substance Use Disorder in the last 3 months except for nicotine and caffeine. Female participants could not be pregnant, breast feeding, or not using medically accepted form of contraception when engaged in sexual intercourse. Finally, veterans could not have received prior Vagus Nerve Stimulation, Electroconvulsive Therapy, or be enrolled in another PTSD treatment study.

## **2.2 Procedures**

2.2.1 Overview: The screening/baseline visit began by acquiring written informed consent.

Subsequently, evaluations to determine safety and appropriateness, as well as clinical ratings and laboratory testing (Urine Drug Screen (UDS) and urine pregnancy testing) were performed.

Those meeting eligibility criteria, including ability to obtain motor threshold, were randomized to 1 Hz versus 10 Hz stratified by significant depression (Montgomery-Asberg Depression Rating Scale (MADRS) (Montgomery and Asberg, 1979) > 19). Participants were treated for 5

days a week for 6 weeks with a 3 week taper (3 treatments per week for 1 week, 2 treatments per week for 1 week, then 1 treatment per week for 1 week). Participants underwent clinical evaluation weekly for clinical effect during the treatment, at the end of the taper and at 1 and 3 months post treatment. In addition, safety was assessed prior to each treatment and/or evaluation.

2.2.2 Screening/Baseline Visit: Participants first were informed about the study and given an opportunity to have all questions answered. When the veteran understood the protocol and was comfortable with participating, written consent was obtained. After consent, the Veteran underwent the following evaluations for safety and to confirm the appropriateness of entry into the trial: basic demographics; Transcranial Magnetic Stimulation and Safety Screen (TASS) (Keel et al., 2001); a history and physical by a TMS credentialed physician; and a UDS for all participants and a urine pregnancy test for all women of child-bearing potential. Clinical evaluations consisted of measures of PTSD, function, depression, traumatic brain injury (TBI), pain, and handedness with the Annette Handedness Scale (Annett, 1970). Clinician Administered PTSD Scale (CAPS-5) (Blake et al., 1995; Weathers et al., 2013) was used for baseline/screening as well as for post treatment evaluation. The CAPS-5 was developed by the National Center for PTSD and has become the "gold standard" for assessing PTSD in individuals over age 15. The evaluation provided a measure of symptom severity and sufficient criteria to determine whether a current diagnosis of PTSD was valid. The PCL-5 was used at the Screening/Baseline visit and during each Clinical Evaluation to assess PTSD symptoms (Blevins et al., 2015; Wortmann et al., 2016). This measure provided a minimum score for PTSD symptom severity as well as a secondary measure of PTSD symptoms. The functional status of veterans was measured using the Inventory of Psychosocial Functioning (IPF) (Rodriguez et al., 2012). The IPF was an 80

question self-report scale that assessed function in the areas of family, work, friendships and socializing, parenting, education, self-care, and romantic relationships with spouse or partner.

The Montgomery-Asberg Depression Rating Scale (MADRS) (Montgomery and Asberg, 1979) and Quick Inventory of Depressive Symptomatology-Self Report version (QIDS-SR) (Rush et al., 2005; Rush et al., 2003) assessed the severity of depressive symptoms. The MADRS score was also used to stratify the randomization (MADRS > 19 for depressed group) as well as a secondary measure of depressive symptoms. The QIDS-SR assessed change in depressive symptoms during the trial. The QIDS-SR was administered during initial screening and during the Clinical Evaluation visits to track any change in depressive symptomatology. In addition, a physical pain score was obtained at baseline/screening and at every Clinical Evaluation. The participant was asked to rate overall physical pain in the last 24 hours on a scale of 0 to 10, with 0 corresponding to no pain and 10 corresponding to the most severe pain ever experienced. The Neurobehavioral Symptom Inventory (NSI) (King et al., 2012) assessed possible post-concussive symptoms associated with mild TBI. The scale is a 22 item self-report measure.

2.2.3 Evaluations: A safety assessment was performed prior to each treatment or at any time clinically indicated (e.g., significant side effect during or between treatments) consisting of asking about: 1) side effects, 2) changes in medication, 3) changes in medical conditions, and 4) changes in psychiatric symptoms (e.g., suicidality, plans to harm others). The Clinical Evaluations were performed after every 5 treatments for first 30 treatments, at the end of treatment taper, and at 1 and 3 month post-treatment follow-ups. The Clinical Evaluations consisted of PCL, QIDS-SR, and pain score on every evaluation visit. The IPF was obtained at baseline, after 15 treatments, after 30 treatments, at the end of treatment, and at the post

treatment 1 and 3 month follow-ups. CAPS, MADRS, and NSI were obtained at baseline/screening and after the 30th treatment.

2.2.4 Repetitive Transcranial Magnetic Stimulation: The veterans were placed in the NeuroStar chair (Neuronetics, Malvern, PA) with hearing protection in place, and the motor threshold (MT) was determined. The MT was defined as the stimulus intensity of stimulation that induces visually perceptible movement of the contralateral (in this case, the left) abductor pollicis brevis (APB) 50% of the time. (Pridmore et al., 1998). Once the spot of maximal contraction was determined, a PEST algorithm (Mishoury et al., 2004) was used to determine the MT four times. The mean of these four MT served as the MT used in the study. After motor threshold determination, a stratified randomization was performed based on significant depressive symptoms, which were defined as a MADRS score > 19. Using a computer randomization schedule, an investigator who was independent of any treatments generated two random lists of active and sham index cards (i.e., with and without significant depression) that were placed in envelopes prior to the trial beginning. When the participant was ready to begin the first treatment, the treater opened the next envelope in line for the appropriate group to determine the randomization assignment. The participant knew the assignment as well as the treater but the investigators assessing all the clinician rating scales were masked to assignment.

After the randomization, the stimulator coil was positioned over the dorsolateral prefrontal cortex - DLPFC (Brodmann Area 9/46). The right dorsolateral prefrontal cortex was targeted using head measurements and a computerized program that provides coordinates for the approximate F4 electrode site under the 10/20 electrode convention (Beam et al., 2009). The dose of rTMS over the DLPFC was 110% of MT. The intensity of 110% MT was chosen as our sample was limited to 18-50 years of age. The 110% MT was thought to be a reasonable option

to balance adequate dose to overcome distance from coil to cortex (Kozel et al., 2000; Nahas et al., 2004) and tolerability. For those randomized to 1 Hz frequency, the 1 Hz rTMS was continuous for 40 minutes for a total of 2400 pulses/session. For those randomized to 10 Hz, rTMS was 4 seconds on and 36 seconds off for 40 minutes for a total of 2400 pulses/session. For both groups, the total number of treatments per participant was 36, and the total number of pulses per participant was 86,400. The interstimulus interval of the 10 Hz group was extended past the standard 26 seconds to 36 seconds in order that the time of treatments was equal for both groups. Both pulse parameters were within the safety profile of rTMS (Rossi et al., 2009; Wassermann, 1998). If subjects were initially intolerant of 110% MT, then the coil could be rotated to find a more tolerable position. If that did not make the rTMS tolerable, then the rTMS output was reduced to 100% of MT to enable the veteran to become used to the stimulation. All participants were quickly raised to 110% MT.

For return TMS visits, participants were interviewed for side effects, medication changes, medical and psychiatric changes. A TMS credentialed physician reviewed any changes prior to treatment. After hearing protection was in place, the TMS coil was positioned based on previous measurement and the patient underwent treatment. Participants were allowed to continue current medications as long as they did not increase the risk of rTMS and were held constant during the six weeks of the trial. Participants were compensated for their time in a prorated manner up to \$350 if all visits were completed.

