### **2.3 Data Analysis**

Data were double entered into an Access database and cross checked for discrepancies prior to analysis. Discrepancies were resolved by returning to primary sources. Descriptive

statistics were reported for the demographic and clinical characteristics of the obtained sample, including age, sex, education, employment, baseline function (IPF), baseline severity of PTSD (CAPS and PCL-5), baseline depression (QIDS-SR, MADRS), baseline pain (Pain Score), and baseline post concussive symptoms (NSI). Categorical variables were expressed as frequencies with percentages, and continuous variables as means with standard deviations. To assess how well the samples were randomized, the two active treatment groups were compared on baseline variables including demographics and the outcomes. No missing data imputation was performed. Chi-square tests and Fisher's Exact Test (whenever cell count is less than 5) were used to compare categorical variables; *t-tests were* used to compare continuous variables within and between groups.

For the primary hypothesis, a Welch two-sample t-test that assumes unequal variances was used to investigate whether 1 Hz rTMS versus 10 Hz rTMS provides a significantly greater improvement in PTSD symptoms (CAPS score) and/or function (IPF score) by 30th treatment. Improvement in an outcome was primarily defined as change in scores from pre-treatment baseline to post 30 treatments. The presence of a significant improvement from baseline to post 30 within each treatment group was also tested by performing a paired t-test.

Secondarily, improvement was also evaluated as the proportion of responders and remitters by post 30 treatments. Response was defined as score reduction of 50% (QIDS-SR and MADRS) or 30% (PCL-5 and CAPS-5). Remission was defined using the following score thresholds: 5 or less for QIDS-SR; 10 or less for MADRS; 33 or less for PCL-5; and no longer meeting criteria of PTSD on the CAPS-5. Other secondary analyses were similarly performed on QIDS-SR, pain, NSI, MADRS and PCL-5 scores.

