### **3. RESULTS**

#### **3.1 Patient population**

Participant recruitment, enrollment, assignment to study conditions, and study retention are presented as a Consort diagram in Figure 1. Forty-four participants were enrolled with data

being acquired from September 2014 until February 2018. Nine veterans were not randomized with six failing to meet diagnostic criteria by CAPS-5, one was determined to have a history of seizures, one was unable to get off work, and one was unable to have motor threshold determined. Of the 35 randomized, 17 were allocated to the 1 Hz group and 18 to the 10 Hz group. Of the 17 veterans in the 1 Hz group, 14 completed the primary endpoint and all subsequent visits. The three participants who did not reach the primary endpoint included two that stopped due to work concerns and one who was lost to follow-up. Of the 18 veterans in the 10 Hz group, 13 completed the primary endpoints with one of those not completing the taper or follow-up visits. The five who did not reach the primary endpoint included two that could not tolerate the first treatment, one stopped due to headaches from another medical condition, one was too frustrated by parking, and one was lost to follow-up. A total of 27 who completed the primary end points constituted the final sample for testing the primary hypothesis, and they had no missing data on the tested outcomes.

- Figure 1 about here –

There were no significant differences between treatment groups on their baseline assessment scores, including demographic and baseline rating scales. (Table 1)

- Table 1 about here –

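### The only post-baseline CAPS is tied to the 30th treatment, with no assessment described for veterans who stop rTMS earlier, so the 1 Hz versus 10 Hz test compares completers only

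*Combined protocol and SAP*

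**What the plan says.** All references are to the combined protocol and SAP.

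- **Endpoint scales.** Section 2.2.3: "CAPS, MADRS, and NSI were obtained at baseline/screening and after the 30th treatment". Section 2.2.2 says more loosely that the CAPS-5 "was used for baseline/screening as well as for post treatment evaluation". No other CAPS time point appears.
- **Other scales.** These also follow the treatment count (section 2.2.3): "The Clinical Evaluations were performed after every 5 treatments for first 30 treatments, at the end of treatment taper, and at 1 and 3 month" follow-up. PCL-5, QIDS-SR and pain are taken at each of these evaluations. For function: "The IPF was obtained at baseline, after 15 treatments, after 30 treatments, at the end of treatment", and at the two follow-ups.
- **Primary endpoint.** Section 2.3: "Improvement in an outcome was primarily defined as change in scores from pre-treatment baseline to post 30 treatments". The primary outcomes are CAPS and IPF. Missing values are not imputed.
- **Early stopping.** No early-termination visit, calendar-based endpoint visit or off-treatment assessment is described.
- **What happened.** Section 3.1 reports 17 randomised to 1 Hz and 18 to 10 Hz, of whom 14 and 13 reached the endpoint. In 1 Hz the three who did not were "two that stopped due to work concerns and one who was lost to follow-up". In 10 Hz the five were "two that could not tolerate the first treatment, one stopped due to headaches from another medical condition, one was too frustrated by parking", and one lost to follow-up. The 27 completers form the sample for the primary test.

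**The concern.** This point is about what is collected, which comes before any question of how missing values are analysed. Because the endpoint visit is triggered by the number of treatments received, stopping treatment and leaving the outcome assessment become in effect one event. A veteran who stops at session 1 or session 20 has no second CAPS due, even if willing to be assessed.

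The randomised question is which frequency gives more improvement. If the schedule drops veterans because they could not tolerate the assigned frequency, membership of the analysis set can depend on the treatment being compared, and the protection of randomisation is weakened. No analysis can recover scores that were never due; it can only make assumptions about them. The trial also loses precision that it could ill afford: section 3.5 says the evaluable sample fell short of the planned 40 and that power for the between-arm comparison was low.

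**Working it through.** **Step 1: reproduce the analysis set.** Inputs are from section 3.1.

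- Randomised: 44 − 9 = 35 = 17 + 18.
- No endpoint: 17 − 14 = 3 (1 Hz) and 18 − 13 = 5 (10 Hz), 8 in total.
- Analysed: 35 − 8 = 27 = 14 + 13, which matches the stated figure.

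**Step 2: classify the eight.**

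| Reason | 1 Hz | 10 Hz |
|---|---|---|
| Work | 2 | 0 |
| Could not tolerate first session | 0 | 2 |
| Headaches from another medical condition | 0 | 1 |
| Parking | 0 | 1 |
| Lost to follow-up | 1 | 1 |
| Total | 3 | 5 |

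Not described as lost: 2 + 4 = 6 of 8. Documented as stopping because of the stimulation: 2, both on 10 Hz.

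**Step 3: do the interim scales fill the gap?** PCL-5, QIDS-SR and pain begin after treatment 5, and IPF after treatment 15. Later stoppers may have some interim values on these scales. The two who stopped at the first session reached none of the scheduled evaluations during treatment. The documents do not say whether the 1- and 3-month follow-ups applied to those who stopped early, and CAPS is not taken at those visits in any case.

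**Step 4: loss by arm.** 3/17 = 17.6% and 5/18 = 27.8%; Fisher's exact test gives p = 0.69.

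**Step 5: what a visit due for everyone could recover.** With equal standard deviations in the two arms, assumed the same for off-treatment scores, the standard error of the arm difference is proportional to √(1/n₁ + 1/n₂). For 14 v 13, 1/14 + 1/13 = 0.1484.

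| Who attends (assumption) | 1 Hz | 10 Hz | Total | SE relative to 14 v 13 |
|---|---|---|---|---|
| As observed | 14/17 (82%) | 13/18 (72%) | 27/35 (77%) | 1 |
| All six (ceiling) | 16/17 (94%) | 17/18 (94%) | 33/35 (94%) | √(0.1213/0.1484) = 0.904 |
| Half of the six, 1 and 2 by arm | 15/17 (88%) | 15/18 (83%) | 30/35 (86%) | √(0.1333/0.1484) = 0.948 |
| Only the three not citing work or parking | 14/17 (82%) | 16/18 (89%) | 30/35 (86%) | √(0.1339/0.1484) = 0.950 |

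**Step 6: power, for illustration.** The documents give no planning effect size, and the Table 2 means and standard deviations are not in the text, so standardised differences are assumed (two-sample t-test, two-sided alpha 0.05, equal standard deviations).

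| Assumed difference | 14 v 13 | 16 v 17 (ceiling) |
|---|---|---|
| 0.5 SD | 23.8% | 28.5% |
| 0.8 SD | 51.5% | 60.5% |
| 1.0 SD | 70.4% | 79.4% |

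The difference detectable with 80% power falls from about 1.12 SD to about 1.01 SD at the ceiling.

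**The case against.** Several objections have force.

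- **A treatment-count endpoint is coherent.** Section 2.3 asks about improvement by the 30th treatment, and sessions, pulses and session time were matched between arms. A visit for everyone randomised answers a different question, closer to treatment policy. This stands as a choice of estimand, but the conclusions should then be limited to completers.
- **The schedule does not forbid assessing those who stop.** A reader might infer an explicit rule that stopping rTMS means leaving the study. No text says so. What can be said is that no such assessment is described and that the primary test used completers only.
- **Attendance is uncertain.** Not being lost to follow-up is not the same as being willing to attend. Work or parking, cited by three of the six, could also hinder an assessment visit. If those three declined and the others came, the imbalance would reverse (82% v 89%) instead of closing.
- **Few stops are attributed to the stimulation.** A reader might count the headache stop as a third, but section 3.1 attributes it to another condition.
- **Much is already disclosed.** Section 3.1 gives the stopping reasons by arm, section 3.4 reports the first-session intolerance, and section 3.5 cautions against firm conclusions from non-significant results.

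A reader might also see a conflict between section 2.2.1, where "Participants underwent clinical evaluation weekly for clinical effect during the treatment", and the every-five-treatments rule in section 2.2.3. At five sessions a week the two coincide, and 30 sessions take six weeks. The endpoint is defined only by treatment count and no missed-session data are given, so the documents do not support a claim that some veterans had a late six-week endpoint.

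**Conclusion.** The concern holds as a weakness of the assessment schedule. CAPS, MADRS and NSI have one post-baseline time point, reachable only by completing 30 treatments, and eight of 35 randomised veterans (23%) have no primary endpoint. Two of the eight stopped because of the stimulation, both on 10 Hz, so exclusion can depend on the assigned frequency.

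The effect is a risk of bias, not a demonstrated one. It would go too far to say that differential dropout is shown, because the arms differ by two people. The precision at stake is modest: a standard error about 5% lower if half of the six attend and about 10% lower at most. These figures rest on assumed attendance and on off-treatment scores having the same variance as the others.

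Section 3.5 nevertheless draws a preliminary inference that a large difference is unlikely. It gives the sample sizes of 14 and 13 but does not limit that inference to veterans who completed 30 treatments.

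**What to change.** **Schedule (successor protocol).** Data collection ended in February 2018, so this cannot be applied to the present trial. Make CAPS, IPF, PCL-5, QIDS-SR and MADRS due at the planned end of the 30-treatment period, about week 6 from randomisation with a stated window, for every randomised veteran whether or not rTMS was stopped, unless consent is withdrawn. State that stopping rTMS is not withdrawal from assessment. Record the number of treatments received as a separate variable, so that an on-treatment analysis remains possible.

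**Cost.** In a trial like this one, at most six more endpoint visits by the masked assessors already in place, within the existing prorated payment. Some who stop will decline, and off-treatment scores will dilute a pure on-treatment contrast.

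**Completed trial.** State beside the primary result, and beside the remark in section 3.5 that a large difference is unlikely, that both apply to the 27 veterans who completed 30 treatments and not to all 35 randomised. This costs one or two sentences.
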